## 6.2. Efficacy Analyses

Efficacy analyses will be performed on the FAS.

Tabulations will be shown per planned treatment group.

### 6.2.1. Level of Significance

Statistical tests for efficacy analysis will be done at a 2-sided significance level of 10%.

### 6.2.2. Primary Efficacy Parameter

The primary efficacy endpoints for this study is the change from baseline in ESSDAI score at Week 12.

The ESSDAI is a systemic disease activity index to assess 12 domains (i.e. organ systems: constitutional, lymphadenopathy, glandular, articular, cutaneous, pulmonary, renal, muscular, peripheral nervous system, CNS, hematological, biological) in patients with pSS, where each of the domains is divided into 3-4 levels of activity. These scores are summed across the 12 domains in a weighted manner to provide the total score (range 0-123). A clinically meaningful reduction from baseline ( $\geq 3$  points) indicates the improvement of symptoms.

The ESSDAI will be assessed at baseline, week 4, week 8 and week 12.

#### 6.2.2.1. Derivation Rules

The binary categorizations of the ESSDAI actual values calculated per visit is defined as follows:

- ESSDAI Responder: Subjects having reduction from baseline  $\geq 3$  points by analysis window

#### 6.2.2.2. Analyses Methods

Analysis will be performed on total score as well as the 12 domain scores for each treatment group and analysis visit. Observed and change from baseline will be summarized using descriptive statistics by treatment group and visit.

An MMRM will be used on the change from baseline to week 12 to compare treatment groups, with a 90% CI of the treatment difference.

The following covariates will be used: treatment-by-visit interaction and baseline-by-visit interaction. An unstructured variance-covariance matrix will be used to model the residuals. If the default Newton–Raphson algorithm used by SAS PROC MIXED fails to converge, the following will be tried to avoid lack of convergence while maintaining an unstructured variance:

- A. The Fisher scoring algorithm (via the SCORING option of the PROC MIXED statement) will be used to obtain the initial values of covariance parameters.
- B. If the above fails, the no-diagonal factor analytic structure will be used which effectively performs the Cholesky decomposition via the TYPE=FA0(V) option of the REPEATED statement, where V is the total number of visits in the response vector (V = 3).
- C. If all the above fails, the variance-and-correlations parameterization will be attempted using TYPE =UNR

In the rare case where all the above fails, the Toeplitz structure with the sandwich variance estimator (EMPIRICAL option) will be used. If this option also fails, the AR(1) + random intercept model will be tried with the sandwich variance estimator.

The LSM, LSM difference between GLPG3970 and the placebo group (reference category), standard error, two-sided 90% CIs for the LSM and difference between treatment groups and p-value for treatment differences will be presented. The number of subjects in the analysis population and number of subjects in the analysis will be provided by treatment group.

Graphs of the mean (+- SE) actual values over time and of the mean (+- SE) change from baseline will be presented. Also, graph of the LSM (+-SE) change from baseline will be provided. In addition, profile plot of the actual values and change from baseline will be provided by treatment group. All values, including unscheduled visits will be presented in profile plot of the actual values. If there are more than one visits on the same day, time will be considered to order them.

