## 1. INTRODUCTION

This statistical analysis plan (SAP) describes the final statistical analyses of study GLPG3970-CL-207. The results of the analysis will be described in the clinical study report (CSR).

Technical details on derivations and mock tables, listings and figures (TLFs) will be presented in a separate document.

The statistical analysis will process and present the results following the International Council for Harmonization (ICH) standards, particularly the ICH-E3, ICH-E6, ICH-E9, ICH-R9 (R1) and ICH-E14 guidelines.

On 26 November 2021, the Safety Monitoring Committee recommended to immediately terminate Study GLPG3970-CL-207 due to a safety signal of liver toxicity. Therefore, the GLPG3970-CL-207 study was prematurely stopped. In view of this, only the primary endpoint and safety analyses will be performed. Results will be presented in an abbreviated CSR. Any provisions no longer applicable following premature study termination are highlighted in grey.

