## 2.6. Sample Size Justification

Up to 30 subjects are planned to be randomized 2:1, i.e. 20 subjects will receive GLPG3970 (400 mg qd) and 10 subjects will receive placebo. In case of drop-outs due to SARS-CoV-2 infection, additional subjects may be randomized on top of the planned sample size. The number of additional subjects randomized will not exceed the number of subjects dropping out of the study in relation to SARS-CoV-2. Randomization of additional subjects will be decided by the sponsor before study lock or related unblinding has occurred.

This sample size provides favorable operating characteristics for the primary efficacy endpoint (i.e. ESSDAI change from baseline at Week 12) in terms of the modified signal detection methodology r. This methodology will be used to provide further insight into the treatment effect of GLPG3970 over placebo, and will support scenario analyses. The posterior distribution of this treatment effect will be estimated, and from this distribution probabilities of reaching at least a certain effect (delta) will be derived, e.g. a range of plausible effect size values going from as high as  $P(\delta \geq -5)$  to as low as  $P(\delta \geq -2)$ . A common standard deviation (SD) of 4 was assumed for both active and placebo arm.

Probability	Reference value	Outcome
0.852	-5	Signal detected
0.041		No conclusion
0.107		Signal not detected
0.427	-3	Signal detected
0.088		No conclusion
0.485		Signal not detected
0.205	-2	Signal detected
0.050		No conclusion
0.745		Signal not detected

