## Appendix XI: SAS Code

### Mixed Model for Repeated Measures

The SAS code for MMRM model with unstructured variance-covariance matrix for the primary efficacy endpoint is:

```
PROC SQL data = dataset NOPRINT;
  SELECT mean(AVAL) INTO :b FROM ADXX where paramcd = 'XXX' and fasfl = 'Y'
  and avisit = 'Baseline';
QUIT;
```

For parameters planned to be collected/measured at Week 4, Week 8 and Week 12 the following SAS code will be used:

```
PROC MIXED data = dataset;
  CLASS subjid trt visit ;
  MODEL change = visit*trt bsl*visit/ NOINT DDFM=KenwardRoger;
  REPEATED visit / SUBJECT=subjid TYPE=un;
  LSMEANS visit*trt / cl alpha=0.1 at (bsl) = (&meanbsl. );
  ESTIMATE 'GLPG3970 vs. Placebo: Week 4' avisit*trtp 1 0 0 -1 0 0 /CL ALPHA = 0.1;
  ESTIMATE 'GLPG3970 vs. Placebo: Week 8' avisit*trtp 0 1 0 0 -1 0 /CL ALPHA = 0.1;
  ESTIMATE 'GLPG3970 vs. Placebo: Week 12' avisit*trtp 0 0 1 0 -0 -1 /CL ALPHA = 0.1;
  ESTIMATE 'AUEC GLPG3970' avisit*trtp 4 4 2 0 0 0 bsl*avisit %sysevalf(4*&meanbsl.)
  %sysevalf(4*&meanbsl.)
  %sysevalf(2*&meanbsl.) / divisor = 12 CL ALPHA = 0.1;
  ESTIMATE 'AUEC Placebo' avisit*trtp 0 0 0 4 4 2 bsl*avisit %sysevalf(4*&meanbsl.)
  %sysevalf(4*&meanbsl.)
  %sysevalf(2*&meanbsl.) / divisor = 12 CL ALPHA = 0.1;
  ESTIMATE 'AUEC GLPG3970 vs. Placebo' avisit*trtp 4 4 2 -4 -4 -2 / divisor = 12 CL
  ALPHA = 0.1;
RUN;
```

Code for endpoints measured at Baseline, Week 8 and Week 12:

```
LSMESTIMATE trt*visit
  'GLPG3970 vs Placebo: Week 8' 1 0 -1 0,
  'GLPG3970 vs Placebo: Week 12' 0 1 0 -1;
RUN;
```

For the log transformed parameters the following will be applied:

- In the *PROC SQL*: *AVAL* will be replaced by *log(AVAL)*
- In the *PROC MIXED*:
  - o *Change* will be replaced by *geopchg=log(aval)-log(bsl)*
  - o And *bsl* will be replaced by *log(bsl)*

If the default Newton–Raphson algorithm used by SAS PROC MIXED fails to converge, the following will be tried to avoid lack of convergence while maintaining an unstructured variance:

- A. The Fisher scoring algorithm (via the SCORING option of the PROC MIXED statement) will be used to obtain the initial values of covariance parameters:

*PROC MIXED data = dataset **SCORING=5**;*

...

The rest of the code is the same as the first full proc mixed code provided.

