- B. If the above fails, the no-diagonal factor analytic structure will be used which effectively performs the Cholesky decomposition via the TYPE=FA0(V) option of the REPEATED statement, where V is the total number of visits in the response vector (V = 3):

*PROC MIXED data = dataset;*

...

*REPEATED visit / subject=subjid type=FA0(3);*

...

The rest of the code is the same as the first full proc mixed code provided.

- C. If all the above fails, the variance-and-correlations parameterization will be attempted using TYPE =UNR:

*PROC MIXED data = dataset;*

...

*REPEATED visit / subject=subjid type=UNR;*

...

The rest of the code is the same as the first full proc mixed code provided.

In the rare case where all the above fails, the Toeplitz structure with the sandwich variance estimator (EMPIRICAL option) will be used:

*PROC MIXED data = dataset **EMPIRICAL**;*

...

*REPEATED visit / subject=subjid type=TOEP;*

...

The rest of the code is the same as the first full proc mixed code provided.

If this option also fails, the AR(1) + random intercept model will be tried with the sandwich variance estimator:

*PROC MIXED data = dataset **EMPIRICAL**;*

...  
*REPEATED visit / subject=subjid type=AR(1);*  

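### Minor and conditional: if the unstructured MMRM and its three rescue attempts all fail, the last-resort models use an uncorrected sandwich standard error, so the Week 12 90% CI tends to be too narrow

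*SAP*

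**What the plan says.** The primary model in SAP 6.2.2.2 is an MMRM on change in ESSDAI at Weeks 4, 8 and 12, with treatment-by-visit and baseline-by-visit terms and an unstructured covariance. Appendix XI gives the main code as "MODEL change = visit*trt bsl*visit/ NOINT DDFM=KenwardRoger". If it does not converge, three attempts (A to C) try to keep the unstructured matrix. After that: "In the rare case where all the above fails", "the Toeplitz structure with the sandwich variance estimator (EMPIRICAL option) will be used". A second last resort follows: "If this option also fails, the AR(1) + random intercept model will be tried with the sandwich variance estimator".

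The Appendix XI code for the first of these adds the plain EMPIRICAL option and "REPEATED visit / subject=subjid type=TOEP", then states "The rest of the code is the same as the first full proc mixed code provided". So the Kenward-Roger line is inherited by reference. No small-sample correction of the sandwich, and no df rule for it, appears in either place.

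On numbers, SAP 2.6 plans that "20 subjects will receive GLPG3970 (400 mg qd) and 10 subjects will receive placebo". SAP 1 reports the early stop and keeps this analysis: "only the primary endpoint and safety analyses will be performed". SAP 4.4.1.2 drops non-PK data from more than 7 days after the last dose from the on-treatment visits. It also allows the MMRM whenever more than 30% of the sample size has data.

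**The concern.** A classical sandwich variance is built from squared residuals, and fitted residuals are smaller than true errors. The shortfall is greatest for subjects with high leverage, which here means the small placebo arm. With 10 placebo subjects or fewer, the standard error is too small on average, so the CI is too short and the p-value too low.

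The main model is protected in small samples by Kenward-Roger. The fallback is not: Kenward-Roger adjusts a model-based covariance, and the SAP does not say what df apply once that covariance is replaced by a sandwich. At stake are the 90% CI and p-value for the primary efficacy endpoint, if this branch is used.

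**Working it through.** **Inputs.** From the SAP: arms of 20 and 10, common SD 4 (2.6), two-sided 10% level (6.2.1), three visits, and treatment and baseline effects at each visit (6.2.2.2). The >30% rule on a base of 30 needs more than 0.3 × 30 = 9, so at least 10 subjects. The documents give neither the number enrolled nor the Week 12 numbers by arm, so every split below 20/10 is assumed.

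**The plan's own figure.** The plan gives no coverage for the fallback. Its only figure at 20/10 is the table in SAP 2.6. There SE = 4 × √(1/20 + 1/10) = 1.549. With a flat prior and an inferred rule (signal if P(δ ≤ −2) ≥ 0.80, that is, an estimate below −3.30), the signal probabilities at −5/−3/−2 are 0.863/0.422/0.200, against the stated 0.852/0.427/0.205. This supports the SD and allocation as inputs. The table does not otherwise bear on the point.

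**Step 1: size of the bias by hand.** With complete data every visit has the same design, so the Week 12 contrast equals a Week 12 ANCOVA whatever the working covariance. Its classical sandwich is HC0, (X′X)⁻¹(Σeᵢ²xᵢxᵢ′)(X′X)⁻¹, with E(eᵢ²) = σ²(1 − hᵢ). Ignoring the baseline term, hᵢ = 1/(arm size), and the expected sandwich variance is 16 × [(n₁−1)/n₁² + (n₀−1)/n₀²]:

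- 20/10: 16 × (19/400 + 9/100) = 2.20, root 1.483, against a true SE of 1.549 (ratio 0.96).
- 7/3: 16 × (6/49 + 2/9) = 5.51, root 2.348, against 4 × √(1/7 + 1/3) = 2.760 (ratio 0.85).

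Estimating the baseline slope makes it worse. In simulation the mean sandwich SE is 1.459 against a true SD of 1.580 at 20/10 (8% too small), and 2.217 against 2.958 at 7/3 (25% too small).

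**Step 2: coverage of the nominal 90% CI, complete data.** 60,000 null trials per split, equal SD 4, error about 0.1-0.2 point:

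| Active/placebo | Classical, t(n−3) | Classical, z | CR2 + Satterthwaite | HC3-type, t(n−3) |
|---|---|---|---|---|
| 20/10 | 87.3% | 86.0% | 90.1% | 91.3% |
| 14/7 | 86.0% | 84.0% | 90.1% | 91.7% |
| 10/5 | 84.1% | 81.0% | 90.3% | 92.1% |
| 7/3 | 79.7% | 74.1% | 91.3% | 92.7% |

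Repeat runs of 12,000 to 20,000 trials agree within 1 point. At 20/10, residual df of 81 gives 86.3% and n−2 gives 87.1%, so no df choice tried restores 90%. With SDs of 4/6 or 6/4 by arm, classical t covers 76.3-87.9% and CR2 88.9-92.7%.

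**Step 3: Toeplitz REML with missing data.** About 3,000 null trials per setting, error about 0.6 point. Assumed correlations are 0.6/0.5/0.6. Each cell gives coverage for visit SDs 4/4/4, then 2/3/4:

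| Randomized; at Week 12 | Classical, t | CR2 + Satterthwaite | Model-based Toeplitz |
|---|---|---|---|
| 20/10; 12/6 | 86.6, 85.3% | 90.0, 89.8% | 90.9, 78.3% |
| 10/5; 6/3 | 80.8, 79.2% | 89.4, 89.3% | 92.6, 80.4% |
| 20/10; 7/3 | 80.8, 80.7% | 88.6, 89.2% | 90.3, 77.5% |

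**Step 4: how often the fallback is reached.** Discrete ESSDAI totals were simulated from the seven eligibility domains with assumed activity and change rates, counting a fit as failed when the unstructured matrix is singular. Counts: 0/20,000 at 20/10 complete; 4/20,000 with 12/6 at Week 12; 134/20,000 with 7/3; 225/20,000 with 10/5 randomized and 6/3 at Week 12. Actual software may fail slightly more often.

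**Step 5: coverage given a singular fit** (slow change, complete data):

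- 7/3: 5,535 of 231,584 trials singular (2.4%). Classical 79.8% (t), 74.1% (z); CR2 92.0%.
- 10/5: 379 of 181,860 singular (0.2%). Classical 88.7% (t), 85.2% (z); CR2 94.2%. The error of 88.7% is √(0.887 × 0.113/379) = 1.6 points, so it is within one standard error of 90%.

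**The case against.** The strongest reply is that this branch hardly matters. The SAP itself calls it rare, and the counts agree. Even in the slow-change 7/3 case, 2.4% × about 10 points of lost coverage is about 0.24 point overall. The coverage figures in steps 2 and 3 come from trials that would almost never reach the fallback. Where the condition was imposed, the shortfall with t is clear only at 7/3. At 10/5 the proposed CR2 interval (94.2%) lies further from 90% than the SAP's t interval (88.7%). The small splits are assumed, and the df the software would use are unknown. SAP 1 says that provisions no longer applicable are shaded grey, but the shading is not visible in the text available, so the fallback paragraph may already be inactive. The study is exploratory, and SAP 6.2.2.3 bases decisions on a separate posterior method.

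All of this limits the severity, and the conditional results rule out a flat claim that the fallback interval is always too narrow. It does not make the rule right: SAP 1 keeps the primary endpoint analysis, and the branch is reached most often when few placebo subjects remain, where the sandwich is at its worst.

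A reader might also infer that the trial's primary CI is itself too narrow. The documents do not support that: the main model is unstructured with Kenward-Roger, and nothing shows that it failed. Nor do they support reading 7/3 as the actual Week 12 numbers. The choice of a sandwich is not in itself a mistake, because it guards against a wrong Toeplitz matrix. Only the missing small-sample correction is at issue.

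**Conclusion.** The point holds as a minor, conditional one. Both last-resort models rest on a classical sandwich with no small-sample correction, and the inherited Kenward-Roger line does not supply one. In general the nominal 90% interval then covers about 86-87% at 20/10, a two-sided error of about 13-14% instead of 10%, and about 74-80% at an assumed 7/3.

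For the ESSDAI total the branch is very unlikely. Among trials that would reach it, clear under-coverage is shown only with about 3 placebo subjects. At 10/5 the t interval cannot be told apart from nominal, while z remains low.

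The sizes rest on normal errors in steps 2 and 3, on assumed domain activity and change rates in steps 4 and 5, and on assumed splits. The AR(1) plus random intercept model is covered only by the complete-data argument; it was not fitted with missing data. No claim is made for the 12 domain scores.

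**What to change.** Add one sentence to SAP 6.2.2.2: in the Toeplitz and AR(1) plus random intercept fallbacks, fixed-effect standard errors use a small-sample bias-corrected sandwich (for example CR2/HC2-type), with CIs and p-values on Satterthwaite df. In Appendix XI, replace plain EMPIRICAL in those two blocks and state the df rule there instead of inheriting the Kenward-Roger line. The replacement code needs to be written and tested. An HC3-type sandwich with t on subjects with Week 12 data minus 3 is a more conservative alternative. Switching to a model-based Toeplitz standard error is not a safe substitute: in step 3 it covered only 77.5-80.4% when the SD rose across visits.

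The cost arises only if the fallback is reached. Against the classical t interval, the mean half-width with CR2 grows from 2.49 to 2.71 at 20/10 (9%), from 3.44 to 4.20 at 10/5 (22%) and from 4.18 to 6.22 at 7/3 (49%). HC3-type gives 2.82 at 20/10 (13%). The CR2 interval may also be somewhat conservative given a singular fit (92.0% at 7/3, 94.2% at 10/5).

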### **Analysis of Binary Endpoint**

The ESSDAI response will be summarized for the OC and NRI using number and percentages by treatment group. Fisher's exact method will be used to compare the GLPG3970 and placebo based on NRI rates. Fisher's exact p-value and 90% modified Santner-Snell confidence interval of the difference in response rates will be presented (In particular, the modification of Santner-Snell methodology proposed by Chang and Zhang in 1999 will be used (score option)). In addition, 90% Clopper-Pearson confidence interval based on NRI rates for each treatment group will be provided.

A frequency plot over time will be provided for the subjects having reduction ESSDAI  $\geq 3$  points.

### 6.2.2.3. Decision Making Methodology

The decision making methodology described by Frewer et al (Frewer, Mitchell, Watkins, & Matcham, 2016) will be used to provide further insight into the treatment effect of GLPG3970 over placebo, and will support scenario analyses.

[figure not shown]
The posterior distribution of this treatment effect will be estimated, and from this distribution probabilities of reaching at least a certain effect (delta) will be derived, e.g., a range of plausible effect size values going from as high as  $P(\delta \leq -5)$  to as low as  $P(\delta \leq -2)$ . A common SD of 4 was assumed for both active and placebo arm.

More details about this analysis will be provided in a separate document. This output will be generated for decision making purposes and will not be part of the CSR.

### 6.2.2.4. Area under the Efficacy Curve (AUEC)

To further explore the data in a slightly different fashion, the area under the efficacy curve (AUEC) based on the MMRM-derived LS-means will be derived for GLPG3970 and placebo. The AUEC will be calculated using the trapezoidal rule as illustrated in [Figure 2](#). A 90% confidence interval and between-group p-value will be derived as well. All will be based on the MMRM model for change from baseline in total and 12 domain scores.

**Figure 2. Graphical illustration, calculation of AUEC.**

### 6.2.3. Secondary Efficacy Parameters

#### 6.2.3.1. EULAR Sjögren's Syndrome Patient Reported Index (ESSPRI) Score

The ESSPRI is a patient self-reported outcome measure to assess dryness, limb pain, fatigue, and mental fatigue, where each of the domains normally reported as 0 (not at all) to 10 (extremely severe). The final ESSPRI score is the average of 3: dryness, pain, and fatigue. A clinically significant reduction from baseline of the ESSPRI score (at least one point or 15% of the baseline value) indicates the improvement of symptoms.

The ESSPRI will be assessed at baseline, week 4, week 8 and week 12.

#### 6.2.3.2. Derivation Rules

The binary categorizations of the ESSPRI actual values calculated at week 12 is defined as follows:

- ESSPRI Responder: Subjects having reduction  $\geq 1$  point from baseline or 15% change (i.e., decrease) from baseline

#### 6.2.3.3. Analyses Methods

Analysis will be performed on average score as well as the 3 domain scores for each treatment group and analysis visit. Observed and change from baseline over time will be summarized using descriptive statistics by treatment group and visit.

The analysis of change from baseline up to week 12 in average and domain scores will use the same method as for analysis of the primary efficacy endpoint as detailed in [section 6.2.2.2](#).

Graphs of the mean (+- SE) actual values over time, mean (+- SE) change from baseline and LSM (+-SE) change from baseline will be presented. In addition, profile plot of the actual values will be provided by treatment group. A frequency plot over time will be provided for the subjects having reduction  $\geq 1$  point from baseline or 15% change (i.e., decrease) from baseline

The analysis of the binary categorizations of ESSPRI at each time point will use same method as for the analysis of ESSDAI binary categorization as detailed in [section 6.2.2.2](#).

To further explore the data in a slightly different fashion, an AUEC based on the MMRM-derived LS-means will be derived for GLPG3970 and placebo as detailed in [section 6.2.2.4](#).

A listing will be provided for the ESSPRI domain scores and the total score along with actual values and change from baseline.

**6.2.4. Other Efficacy Parameters**

6.2.4.1. [REDACTED]

[REDACTED]

6.2.4.2. [REDACTED]

[REDACTED]

6.2.4.2.1 [REDACTED]

[REDACTED]

6.2.4.2.2 [REDACTED]

[REDACTED]

[figure not shown]
6.2.4.3. [REDACTED]

[REDACTED]

6.2.4.3.1 [REDACTED]

[REDACTED]

**6.2.4.3.2** [REDACTED]

[figure not shown]
**6.2.4.4.** [REDACTED]

[figure not shown]
**6.2.4.4.1** [REDACTED]

**6.2.4.4.2** [REDACTED]

**6.2.4.5.** [REDACTED]

6.2.4.5.1 [REDACTED]

[REDACTED].

6.2.4.5.2 [REDACTED]

[REDACTED]

6.2.4.6. [REDACTED]

[REDACTED]

6.2.4.6.1 [REDACTED]

[figure not shown]
[REDACTED]

6.2.4.6.2 [REDACTED]

[figure not shown]
[REDACTED]

6.2.4.7. [REDACTED]

[figure not shown]
[REDACTED]

[figure not shown]
6.2.4.7.1 [REDACTED]

6.2.4.7.2 [REDACTED]

6.2.4.8. [REDACTED]

6.2.4.8.1 [REDACTED]

-

-

-

